6.11.1 Analysis of primary efficacy endpoint

50% responder rate for partial onset seizure with or without secondary generalization

Seizure frequency during the screening period and seizure frequency during the maintenance period in 50% responders, defined as subjects achieving at least 50% reduction in the frequency of partial onset seizures with or without secondary generalization during the maintenance period compared to baseline, are presented using descriptive statistics (number of subjects, mean, standard deviation, median (minimum, maximum), 1st quartile, and 3rd quartile), rate, and 95% CI. Seizure frequency is calculated as follows.

6.11.2 Analysis of secondary efficacy endpoints

1) 75% responder rate for partial onset seizure with or without secondary generalization

Seizure frequency during the screening period and seizure frequency during the maintenance period in 75% responders, defined as subjects achieving at least 75% reduction in the frequency of partial onset seizures with or without secondary generalization during the maintenance period compared to baseline, are presented using descriptive statistics (number of subjects, mean, standard deviation, median (minimum, maximum), 1st quartile, and 3rd quartile), rate, and 95% CI. Seizure frequency is calculated as follows.

2) 100% responder (seizure-free) rate for partial onset seizure with or without secondary generalization

Seizure frequency during the screening period and seizure frequency during the maintenance period in 100% responders (seizure-free subjects), defined as subjects achieving 100% reduction in the frequency of partial onset seizures with or without secondary generalization during the maintenance period compared to baseline, are presented using descriptive statistics (number of subjects, mean, standard deviation, median (minimum, maximum), 1st quartile, and 3rd quartile), rate, and 95% CI. Seizure frequency is calculated as follows.

3) Percent change from baseline in the frequency of partial onset seizure with or without secondary generalization during the titration period and maintenance period

Frequency of partial onset seizure with or without secondary generalization during the screening period, titration period, and maintenance period is presented using descriptive statistics (number of subjects, mean, standard deviation, median (minimum, maximum), 1st quartile, and 3rd quartile). Also, percent change in the frequency of partial onset seizure with or without secondary generalization during the titration period and maintenance period compared to the screening

period is calculated and presented using descriptive statistics (number of subjects, mean, standard deviation, median (minimum, maximum), 1st quartile, and 3rd quartile) along with corresponding 95% CI. Seizure frequency is calculated as follows.

4) 50% responder rate for secondary generalized tonic-clonic seizure

Seizure frequency during the screening period and seizure frequency during the maintenance period in 50% responders, defined as subjects achieving at least 50% reduction in the frequency of secondary generalized tonic-clonic seizure during the maintenance period compared to baseline, are presented using descriptive statistics (number of subjects, mean, standard deviation, median (minimum, maximum), 1st quartile, and 3rd quartile), rate, and 95% CI. Seizure frequency is calculated as follows.

5) 75% responder rate for secondary generalized tonic-clonic seizure

Seizure frequency during the screening period and seizure frequency during the maintenance period in 75% responders, defined as subjects achieving at least 75% reduction in the frequency of secondary generalized tonic-clonic seizure during the maintenance period compared to baseline, are presented using descriptive statistics (number of subjects, mean, standard deviation, median (minimum, maximum), 1st quartile, and 3rd quartile), rate, and 95% CI. Seizure frequency is calculated as follows.

6) 100% responder (seizure free) rate for secondary generalized tonic-clonic seizure

Seizure frequency during the screening period and seizure frequency during the maintenance period in 100% responders (seizure-free subjects), defined as subjects achieving 100% reduction in the frequency of secondary generalized tonic-clonic seizure during the maintenance period compared to baseline, are presented using descriptive statistics (number of subjects, mean, standard deviation, median (minimum, maximum), 1st quartile, and 3rd quartile), rate, and 95% CI. Seizure frequency is calculated as follows.

7) Percent change from baseline in the frequency of secondary generalized tonic-clonic seizure during the titration period and maintenance period

Frequency of secondary generalized tonic-clonic seizure during the screening period, titration period, and maintenance period is presented using descriptive statistics (number of subjects, mean, standard deviation, median (minimum, maximum), 1st quartile, and 3rd quartile). Also, percent change in the frequency of secondary generalized tonic-clonic seizure during the

titration period and maintenance period compared to the screening period is calculated and presented using descriptive statistics (number of subjects, mean, standard deviation, median (minimum, maximum), 1st quartile, and 3rd quartile) along with corresponding 95% CI. Seizure frequency is calculated as follows.

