9.7.1.2 Definitions of Analysis Sets

The Safety Analysis Set is the group of subjects who received at least 1 dose of study drug and had at least 1 postdose safety assessment.

The Full Analysis Set is the group of subjects who received at least 1 dose of study drug and had at least 1 postdose primary efficacy measurement.

The Per Protocol Analysis Set is the group of subjects who sufficiently complied with the protocol. Details of the evaluability criteria will be determined before database lock and will be specified in the SAP.

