5.1 Efficacy Analysis Set

Efficacy is analyzed primarily in the Full Analysis Set (FAS), and secondarily in the Per-Protocol Set (PPS). Safety is analyzed in the Safety Analysis Set.

- FAS: subjects who received at least one dose of investigational product and were assessed for primary efficacy at least once during the maintenance period (Week 12 - 5 days ~ Week 36 + 7 days).
- PPS: subjects in FAS who completed the study per protocol without major violation. Subjects who meet any of the following conditions are excluded from PPS.
 - 1) Deviation from selection criteria
 - 2) Use of prohibited concomitant medication or therapy
 - 3) Withdrawal
 - 4) Deviation from treatment compliance
 - 5) Other deviation considered as major protocol violation

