6.11 Efficacy Analysis

In the efficacy analyses, seizure frequency is calculated as follows.

- Seizure frequency during the screening period = (number of seizure / (date of Visit 1 – date of 8 weeks prior to Visit 1)) x 28
- Seizure frequency during the titration period = (number of seizure / (date of end of Visit 3 or date of withdrawal during the titration period – date of start of Visit 2)) x 28
- Seizure frequency during the maintenance period = (number of seizure / (date of end of Visit 5 or date of withdrawal during the maintenance period – date of start of Visit 4)) x 28

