6.12.5 Physical Measurement (Body Weight)

Results at baseline (Visit 1), Week 36 (Visit 5), end-of-study visit, and follow-up as well as the change from baseline to each timepoint post-treatment are presented using descriptive statistics (number of subjects, mean, standard deviation, median, minimum, and maximum).

7. Plan for Revision of Analysis Method

Revision of analysis method is not planned.

8. TLF shell

List of Tables

Table	Table Description
-------	-------------------

Number	
s1	14.1.1 Subject Disposition - All Enrolled Subject
s2	14.1.2 Subject Disposition by Study Site - All Enrolled Subject
s3	14.1.3 Major Protocol Deviations - All Enrolled Subject
s4	14.1.4 Analysis Sets - All Enrolled Subject
b1	14.1.5 Demographic Characteristics - Full Analysis Set
b2	14.1.6 Baseline Disease Characteristics - Full Analysis Set
b3	14.1.7 Past Medical History - Full Analysis Set
b4	14.1.8 Current Medical History - Full Analysis Set
b5	14.1.9 Previous Medications - Full Analysis Set
b6	14.1.10 Concomitant Medications - Full Analysis Set
b7	14.1.11 Previous Medications (anti-epileptic drugs) - Full Analysis Set
b8	14.1.12 Concomitant Medications (anti-epileptic drugs) - Full Analysis Set
b9	14.1.13 Concomitant Non-Pharmacological Therapy - Full Analysis Set
e1_1	14.2.2.1 50% Responder Rate for Partial Onset Seizures with or without Secondary Generalization - Full Analysis Set
e1_2	14.2.2.2 50% Responder Rate for Partial Onset Seizures with or without Secondary Generalization - Per Protocol Set
e2_1	14.2.3.1 75% Responder and 100% Responder (Seizure-Free) Rate for Partial Onset Seizures with or without Secondary Generalization - Full Analysis Set
e2_2	14.2.3.2 75% Responder and 100% Responder (Seizure-Free) Rate for Partial Onset Seizures with or without Secondary Generalization - Per Protocol Set
e3_1	14.2.4.1 Percent Change in the Frequency of Partial Onset Seizures with or without Secondary Generalization during the Titration Period and Maintenance Period compared to Screening Period - Full Analysis Set
e3_2	14.2.4.2 Percent Change in the Frequency of Partial Onset Seizures with or without Secondary Generalization during the Titration Period and Maintenance Period compared to Screening Period - Per Protocol Set
e4_1	14.2.5.1 - 50% Responder, 75% Responder, and 100% Responder (Seizure-Free) Rate for Secondary Generalized Tonic-Clonic Seizure - Full Analysis Set

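### Titration-period percent change is reported only for subjects who reach about Week 12, so the titration diaries of earlier withdrawals go unused

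*SAP*

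**What the plan says.** Protocol 9.7.1.1.2 lists percent change in seizure frequency in the Titration and Maintenance Periods as a secondary endpoint, for total seizures and for secondarily generalized tonic-clonic seizures. SAP 6.11.2 item 3 covers "percent change in the frequency of partial onset seizure with or without secondary generalization during the titration period and maintenance period"; item 7 is the parallel item for secondarily generalized seizures.

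SAP 6.11 ends the titration interval at "date of end of Visit 3 or date of withdrawal during the titration period" and begins it at the start of Visit 2.

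The analysis population comes from elsewhere. SAP 5.1 states: "Efficacy is analyzed primarily in the Full Analysis Set (FAS), and secondarily in the Per-Protocol Set (PPS". Its FAS admits dosed subjects who "were assessed for primary efficacy at least once during the maintenance period (Week 12 - 5 days ~ Week 36 + 7 days"), and the second set is narrower: "PPS: subjects in FAS who completed the study per protocol without major violation", with withdrawal listed as a reason for exclusion. In the table list (SAP 8), e3_1 and e5_1 report the percent change "during the Titration Period and Maintenance Period compared to Screening Period - Full Analysis Set". Tables e3_2 and e5_2 repeat it on the PPS.

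Protocol 9.7.1.2 defines the FAS as subjects who "received at least 1 dose of study drug and had at least 1 postdose primary efficacy measurement" and names no period. SAP 6.3 imputes nothing, and SAP 6.7 plans no sensitivity analysis.

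**The concern.** A summary of what happened during titration should use the subjects who were treated and observed during titration. Here a subject who stops at Week 8 with a complete diary has a measured titration frequency but falls outside both efficacy sets. This differs from the primary endpoint, where such a subject has no maintenance data at all. In this case the outcome exists and is set aside.

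The loss may not be neutral. Protocol 9.1.2 discontinues subjects who cannot tolerate 4 mg, and protocol 9.5.5 lists inadequate therapeutic effect among the reasons for stopping. If those who leave early had less seizure reduction than those who stay, the reported titration change looks better than it was in the treated group. No planned table would show this.

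**Working it through.** **1. The plan's own figures.** Inputs from protocol 9.7.2 and SAP 3: assumed rate 0.353, reference 0.193, normal quantiles 1.96 and 1.282, drop-out 10%.

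- n = (1.96 + 1.282)² × 0.353 × 0.647 / (0.353 − 0.193)² = 93.77, rounded up to 94.
- 94 / (1 − 0.10) = 104.4, rounded up to 105.

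Both stated figures reproduce. The planned allowance is 105 − 94 = 11 subjects (10.5%) over the whole study. The documents do not split it by period.

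**2. The FAS window.** Week 12 is Day 84 and Week 36 is Day 252 (protocol Table 2). The window opens on 84 − 5 = Day 79 and closes on 252 + 7 = Day 259.

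**3. Who reaches the titration column.**

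| Source | Effect on a subject who withdraws in titration before Day 79 |
|---|---|
| Protocol 9.5.1.2 and Table 2 | Diary kept in titration; reviewed at Visits 2 and 3 and at discontinuation |
| SAP 6.11 | Interval can end at withdrawal |
| SAP 5.1, FAS | Excluded: no assessment inside the window |
| SAP 5.1, PPS | Excluded: subset of FAS, and withdrawals removed |
| SAP 8, e3 and e5 | FAS and PPS only |

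The withdrawal branch in SAP 6.11 is thus usable essentially only for withdrawals from Day 79 to the end of titration. A diary reviewed at a discontinuation or follow-up visit after Day 79 might be argued to qualify a subject; the SAP does not say.

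**4. The start of the interval.** If the start of Visit 2 means the Week 6 visit date (Day 42), the formula covers 84 − 42 = 42 of 84 titration days for a subject who stays. For a withdrawal on Day 28 it gives 28 − 42 = −14 days. That conflicts with protocol 9.7.1.5, which bases frequency on the full interval. If the phrase instead means the start of the diary period reviewed at Visit 2, the interval begins at first dose and the problem disappears. Withdrawals between Day 42 and Day 79 have a positive interval on either reading and are still excluded.

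**5. Size.** With k leavers among 105 dosed subjects, all with diary data:

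mean in all dosed − mean in retained = (k / 105) × (mean in leavers − mean in retained).

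The values of k and the difference below are assumptions. The case k = 11 puts the whole planned drop-out into titration before Day 79.

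| k | Share of 105 | Leavers 20 points worse | 40 points worse | 60 points worse |
|---|---|---|---|---|
| 5 | 4.8% | 0.95 | 1.90 | 2.86 |
| 11 | 10.5% | 2.10 | 4.19 | 6.29 |
| 21 | 20.0% | 4.00 | 8.00 | 12.00 |

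If k is 0, or leavers do not differ from retained subjects, the shift is 0. If leavers did better, the sign reverses. For e5_1 the same formula applies, with counts taken among subjects who have baseline secondarily generalized seizures; the documents do not give that number.

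**6. A hazard in the remedy.** Inclusion criterion 4 requires at least 2 seizures in 8 weeks, so the lowest baseline is 2 / 56 × 28 = 1 per 28 days. One seizure in a 3-day diary is 1 / 3 × 28 = 9.33 per 28 days, a change of (9.33 − 1) / 1 = +833%.

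**The case against.** **One cohort keeps the two columns comparable, and the stakes are modest.** These are descriptive secondary summaries with no test. If the SD of percent change were 45 (an assumption), the 95% half-width for a mean with n = 94 would be about 1.96 × 45 / √94 = 9 points, wider than any shift in the 11-leaver row. This stands, and is a reason to show the current-FAS result alongside. It does not justify showing only that result.

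**The protocol does not clearly require the wider set.** Its FAS asks for a post-dose primary efficacy measurement, and the primary variable is defined on the Maintenance Period. The SAP window can be read as a clarification. This stands in part: the protocol names no window, but it is not clear authority for including titration-only subjects. The case rests on matching the population to the period described.

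**A reader might infer that SAP 5.1 and 6.11 contradict each other.** They do not strictly do so. A general formula contains a branch that the analysis set makes nearly unreachable.

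**A reader might infer that the titration effect is overstated.** The documents report no seizure outcomes for titration leavers, and a subject who stops for intolerance may have had good seizure control.

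**A reader might take 17.6% as a withdrawal rate**, from the 82.4% tolerating 4 mg/day in study 206 (protocol 7.3.3.2). That is a tolerability share, identical on placebo, so it is neither a titration withdrawal rate nor an upper bound.

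**Short diaries can dominate a mean.** This stands, as step 6 of the working shows, and the fix must deal with it.

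**Conclusion.** The concern holds as a mismatch between the endpoint and its population. For both seizure categories, the titration-period change is estimated only in subjects assessed at Day 79 or later, although data from earlier withdrawals are collected. The estimate is conditional on staying through titration, and the plan neither says so nor checks the effect.

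The size is unknown from the documents. A shift of about 1 to 12 points in the mean rests on assuming 5 to 21 leavers of 105, each group 20 to 60 points worse than those retained. With the planned 11 all leaving before Day 79, it is about 2 to 6 points. The shift is zero if leavers do not differ, and the direction itself is an assumption. It is worth correcting because the correction is cheap. The primary endpoint and the sample size of 94 (105 enrolled) are not affected.

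**What to change.** In SAP 6.11.2 items 3 and 7 and tables e3_1 and e5_1:

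- Run the titration column on all dosed subjects with baseline and post-dose titration diary data; for e5_1, on those of them with baseline secondarily generalized seizures.
- In SAP 6.11, define the titration interval as first dose (Visit 1) to Visit 3 or to withdrawal during titration, replacing the ambiguous Visit 2 start. The population change cannot be carried out for withdrawals up to Week 6 without this.
- Keep the current FAS for the maintenance column and print N for each column.
- Also show the titration result in the current FAS, so that the two periods can be compared in the same subjects.
- Make the median and quartiles the main summary of percent change, or pre-specify a minimum diary length.

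The cost is SAP wording and a rerun of two tables on data already collected, with no imputation. The downside is that N differs between columns and short diaries add noise.

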6.12 Safety Analysis

6.12.1 Extent of Exposure

With regard to extent of exposure during the study period, duration of treatment and total dose in the titration period and maintenance period are calculated as follows and presented using descriptive statistics (number of subjects, mean, standard deviation, median, minimum, and maximum).

Duration of treatment in the titration period (days)

$$= \text{date of last dose} - \text{date of first dose} + 1$$

Duration of treatment in the maintenance period (days)

$$= \text{date of last dose} - \text{date of first dose} + 1$$

Total dose (mg) = sum of doses administered (daily dose x number of dosing days)

6.12.2 Adverse Events

Treatment-emergent adverse events (TEAEs) were analyzed (TEAEs refer to adverse events that were absent before study treatment and emerged after study treatment, or adverse events that were present before study treatment and worsened after study treatment). Subjects who experienced more than one TEAE are counted once.

ADRs are related adverse events considered as probably related or possibly related by the investigator, for which causal relationship to the investigational product cannot be ruled out. Those considered as not related by the investigator are defined as unrelated adverse events.

Incidence of TEAEs, ADRs, SAEs, and AEs leading to treatment discontinuation is presented using frequency and percentage along with 95% CI.

AEs, ADRs, SAEs, and AEs leading to treatment discontinuation are coded using SOC (System Organ Class) and PT (Preferred Term) of MedDRA and analyzed by causality and severity. Represented codes are presented using the number of subjects and incidence. Listing will be

provided for SAEs.

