7.3.4 Common Adverse Events

In Phase II (study 206 and 208) and Phase III clinical trials (study 304, 305 and 306) of perampanel in treatment-resistant patients, the most TEAEs were CNS-related and not dose-

dependent. Many AEDs suppress the neuronal hyperexcitability pathologically, and subsequent adverse reactions in the CNS are not unexpected. Most AEDs are known to cause sedation, incoordination, drowsiness, fatigue and nausea, and these AEs are mainly dose-related.³⁷ The most common adverse drug reactions (ADRs) of perampanel were dizziness, fatigue, somnolence, nausea, irritability and falls. Perampanel treated patients had higher frequency of depression and aggression than patients taking placebo, with particularly at higher doses. The majority of TEAE severities were mild and moderate, with a relatively low incidence of SAEs. Patients taking perampanel had greater rate of side effects in psychiatrics than with placebo, primarily irritability.

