9.7.1.7.2 ADVERSE EVENTS

The AE verbatim descriptions (investigator terms from the CRF) will be classified into standardized medical terminology using the Medical Dictionary for Regulatory Activities (MedDRA). Adverse events will be coded to the MedDRA (most recent version) lower level term (LLT) closest to the verbatim term. The linked MedDRA preferred term (PT) and primary system organ class (SOC) are also captured in the database.

A TEAE is defined as an AE that emerges during treatment, having been absent at pretreatment (Baseline) or

- Reemerges during treatment, having been present at pretreatment (Baseline) but stopped before treatment, or
- Worsens in severity during treatment relative to the pretreatment state, when the AE is continuous.

Only those AEs that are treatment-emergent will be included in summary tables. All AEs, treatment-emergent or otherwise, will be presented in subject data listings.

The incidence of TEAEs will be reported as the number (percentage) of subjects with TEAEs by SOC and PT. A subject will be counted only once within an SOC and PT, even if the subject experienced more than 1 TEAE within a specific SOC and PT. The number (percentage) of subjects with TEAEs will also be summarized by maximum severity (mild, moderate, or severe).

The number (percentage) of subjects with TEAEs will also be summarized by relationship to study drug (Yes [related] and No [not related]).

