e4_2	14.2.5.2 - 50% Responder, 75% Responder, and 100% Responder (Seizure-Free) Rate for Secondary Generalized Tonic-Clonic Seizure - Per Protocol Set

CONFIDENTIAL

e5_1	14.2.6.1 Percent Change in the Frequency of Secondary Generalized Tonic-Clonic Seizure during the Titration Period and Maintenance Period compared to Screening Period - Full Analysis Set
e5_2	14.2.6.2 Percent Change in the Frequency of Secondary Generalized Tonic-Clonic Seizure during the Titration Period and Maintenance Period compared to Screening Period - Per Protocol Set
ex1	14.3.1 Extent of Exposure - Safety Analysis Set
a1	14.3.2 Summary of Adverse Events - Safety Analysis Set
a2	14.3.3 Incidence of Treatment-Emergent Adverse Events by System Organ Class - Safety Analysis Set
a3	14.3.4 Incidence of Treatment-Emergent Adverse Drug Reactions by System Organ Class - Safety Analysis Set
a4	14.3.5 Incidence of Treatment-Emergent Serious Adverse Events by System Organ Class - Safety Analysis Set
a5	14.3.6 Incidence of Adverse Events Leading to Treatment Discontinuation by System Organ Class - Safety Analysis Set
a6	14.3.7 List of Treatment-Emergent Serious Adverse Events - Safety Analysis Set
a7	14.3.8 Incidence of Treatment-Emergent Adverse Events by System Organ Class and Severity - Safety Analysis Set
a8	14.3.9 Incidence of Treatment-Emergent Adverse Events by System Organ Class and Causality - Safety Analysis Set
l1	14.4.1.1 Hematology - Safety Analysis Set
l2	14.4.1.2 Blood Chemistry - Safety Analysis Set
l3	14.4.1.3 Urinalysis - Safety Analysis Set
l4	14.4.2 Urinalysis: Normal/Abnormal - Safety Analysis Set
l5	14.4.3.1 Hematology: LNH - Safety Analysis Set
l6	14.4.3.2 Blood Chemistry: LNH - Safety Analysis Set
l7	14.4.3.3 Urinalysis: LNH - Safety Analysis Set
v1	14.4.4 Vital Signs - Safety Analysis Set
pe1	14.4.5 Physical Measurement (Body Weight) - Safety Analysis Set

9. Roles and Responsibilities

Role	Name	Responsibility
Biostatistician	PPD	Statistical analysis
QC Biostatistician	PPD	Quality control for the statistical analysis process

10. Applied SOPs

SOP No.	SOP Version	SOP Name
0400	2.0_23-Oct-2017	Statistical Analysis Plan
0401	3.0_01-Jun-2017	Statistical Analysis Process

11. Applied SOP SDs

SD No.	SD Version	SD Title
SD 0400 A	2.0_03-May-2018	Statistical Analysis Plan
SD 0408 A	3.0_23-Oct-2017	STAT Master File Index

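### The SAP's definition of a treatment-emergent AE omits the protocol's limb for events that stopped before treatment and re-emerge, and the SAP plans no listing of all AEs

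*SAP*

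**What the plan says.** Protocol 9.7.1.7.2 gives three routes to a TEAE. The first is an event that appears on treatment and was absent at baseline. The second is an event that "Reemerges during treatment, having been present at pretreatment (Baseline) but stopped before treatment". The third is an event that "Worsens in severity during treatment relative to the pretreatment state, when the AE is continuous". Summary tables are confined to TEAEs, but listings are not: "All AEs, treatment-emergent or otherwise, will be presented in subject data listings".

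SAP 6.12.2 opens by saying that TEAEs are what was analysed and defines them as "adverse events that were absent before study treatment and emerged after study treatment, or adverse events that were present before study treatment and worsened" after it. There is no re-emergence limb, and no reason is given for leaving it out. The only AE listing promised in that section is one for SAEs. In the list of outputs in SAP section 8 this becomes item a6, "14.3.7 List of Treatment-Emergent Serious Adverse Events - Safety Analysis Set". No listing of all AEs appears there.

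**The concern.** Protocol 9.7.1 leaves further detail to the SAP. A narrower rule for which events count is a change to a stated definition, not a detail. Safety is the first secondary objective. The study has one arm, so no control group shares an undercount.

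Recurrences are plausible in this population. Every subject already takes an antiepileptic drug, and Protocol 7.3.4 names fatigue and nausea both as effects of most such drugs and as common reactions to perampanel. The same section notes that "Perampanel treated patients had higher frequency of depression and aggression than patients taking placebo, with particularly at higher doses". A subject who had such an event before, recovered, and has it again on perampanel is someone the protocol means to count. If the tables drop that subject and no full listing is produced, a reader of the SAP's outputs has no way to see the event.

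**Working it through.** The point rests on text, so the first step is to run each type of event through both definitions, reading the SAP literally (*before study treatment* meaning at any earlier time).

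| Event | Protocol 9.7.1.7.2 | SAP 6.12.2 |
|---|---|---|
| Never present before, appears on treatment | Counted (new) | Counted |
| Stopped before treatment, returns at same or lower severity | Counted (re-emergence) | **Not counted**: neither absent before nor worsened |
| Stopped before treatment, returns more severe | Counted (re-emergence) | Counted (worsened) |
| Continuous, becomes more severe | Counted (worsening) | Counted |
| Ongoing, unchanged | Not counted | Not counted |
| Ongoing, worse in some respect other than severity | Not counted | Can be counted: *worsened* is unqualified |

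The second row is the conflict. The last row shows that on the worsening limb the SAP is the wider of the two.

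Next, the outputs. Of the eight AE items in SAP section 8, six carry the treatment-emergent limit in their titles: a2, a3, a4, a6, a7 and a8. Two do not: a1 (the AE summary) and a5 (AEs leading to discontinuation). The opening sentence of 6.12.2 may extend the limit to those two, but the SAP does not say so. A non-serious recurrence from the second row is absent from a2, a3, a7 and a8 and has no listing in the SAP to fall back on.

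Finally, the size. The documents give no recurrence rate, so what follows is an assumed range. Let k be the number of subjects with a same- or lower-severity recurrence, with k from 1 to 10, and take the planned 105 subjects as the denominator.

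- One preferred term, upper bound (all k recurrences in that term, and none of these subjects otherwise counted in it): k/105, so 1/105 = 0.95 to 10/105 = 9.52 percentage points.
- Overall TEAE incidence changes only for subjects with no other TEAE. The protocol's introduction gives the share of perampanel subjects with at least one event as 66.7% in study 206, and 86.0% to 91.8% in studies 304 and 305. If those shares applied here, independently of recurrence, the loss is k × (1 − share)/105.
  - Smallest: 1 × 0.082/105 = 0.08 percentage points.
  - Largest: 10 × 0.333/105 = 3.17 percentage points.
  - With k = 10 and the 86.0% share: 10 × 0.140/105 = 1.33 percentage points.

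**The case against.** The best reply is that a resolved event can be read as absent when treatment starts. On that reading the SAP's first limb covers recurrences and nothing is lost. The SAP also specifies no matching of AE records to medical history, which the literal reading would need. This stands as a possible reading, but the SAP does not state it, and two programmers could reach different counts. The protocol's explicit limb removes the doubt.

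A second reply is that few pre-treatment AEs will be on record. The schedule's footnote h collects AEs from the start of study drug, while Protocol 9.5.1.4.1 starts at consent. Consent is usually given at Visit 1, and the first dose is taken at bedtime that day. Pre-treatment status will therefore come almost wholly from medical history. In addition, the recurrence criterion in 9.5.1.4.1 names only conditions not present before treatment, so some recurrences may never be recorded as AEs. That is a matter for the protocol. The first criterion in that section is broad enough to admit most of them.

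A reader might infer that recurrences vanish from every AE table and every listing. The documents do not support that. The titles of a1 and a5 are not limited, 6.12.2 promises an SAE listing without restriction, more severe recurrences still count, and nothing in the SAP withdraws the protocol's all-AE listing. The list in SAP section 8 is headed as a list of tables, so silence there is an omission and not a cancellation.

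**Conclusion.** The two definitions conflict and need to be reconciled. On a literal reading of SAP 6.12.2, same- or lower-severity recurrences of events that had stopped can fall out of six of the eight AE outputs. The position of a1 and a5 is open. Separately, the SAP's planned outputs do not include the all-AE listing that the protocol commits to.

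The size is unknown. Under the assumed 1 to 10 affected subjects, the effect on overall TEAE incidence is roughly 0.1 to 3 percentage points. A single preferred term could lose up to about 10 points at the extreme. These figures show scale only.

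A reader might also infer that the SAP's definition always favours the drug. Omitting the re-emergence limb can only lower counts, but the SAP's unqualified worsening limb can raise them, so the net direction against the protocol is not fixed.

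**What to change.** Three changes to the SAP before database lock:

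1. In 6.12.2, replace the definition with the protocol's three limbs, including re-emergence of events that had stopped before treatment. Apply it to a2, a3, a4, a6, a7 and a8.
2. State whether a1 and a5 are limited to TEAEs.
3. Add to section 8 a subject listing of all AEs, with a flag for treatment-emergent status.

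The cost is one flag and one listing. SAP 6.9 already separates past history from ongoing conditions, which is the information the re-emergence limb mainly needs. Whether the history form also holds stop dates and severity should be checked, because the documents do not say. Reported AE rates may become slightly less favourable. Taking over the protocol's worsening limb, which is confined to severity and to continuous events, could offset part of that.
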